Nintedanib was also investigated in a Phase III trial in patients with Chronic Fibrosing ILDs with a Progressive Phenotype (332 patients treated with nintedanib 150 mg bid and 331 patients treated with placebo). Nintedanib significantly reduced the annual rate of decline in FVC [mL/year] over 52 weeks compared with placebo in both co-primary populations ($p<0.0001$), namely the overall population and patients with HRCT with Usual Interstitial Pneumonia (UIP)-like fibrotic pattern. The results in the complementary population were consistent. The treatment effect was independent of HRCT pattern (interaction p -value 0.2268). The adjusted differences for the annual rate of decline represent relative reductions of 57% in the overall population, 61% in patients with HRCT with UIP-like fibrotic pattern, and 49% for patients with other HRCT fibrotic patterns. Analyses of time-to-event endpoints indicated reductions in clinically meaningful outcome events and provided supportive evidence for a slowing of disease progression by nintedanib [[c26471552-02](#)].

The observed safety profile of nintedanib in patients with progressive fibrosing ILD comprised risks that were manageable or occurred at a low frequency. The most frequently reported AEs were gastrointestinal disorders, in particular diarrhoea, nausea, and vomiting. Common AEs were mostly mild or moderate in intensity. In addition, treatment with nintedanib was associated with elevations in liver enzymes. The large majority of liver

enzyme elevations normalised upon treatment interruption, dose reduction, treatment discontinuation, or spontaneously with continued treatment.

More details on nintedanib can be found in the Investigator's Brochure [[c01783972](#)].

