3.3 SELECTION OF TRIAL POPULATION

A total of approximately 90 patients with Chronic Fibrosing ILDs with a Progressive Phenotype will be randomized (60 in the active dose group and 30 in placebo) in China. It is planned to randomize approximately two thirds of patients with UIP-like HRCT fibrotic pattern. This will allow for a certain enrichment of patients with more rapid progression, as has been shown in INBUILD. Patients with clinical diagnosis of IPF will be excluded from the current study.

Screening of patients for this trial is competitive, i.e. screening for the trial will stop at all sites at the same time once a sufficient number of patients has been screened. Investigators will be notified about screening completion and will then not be allowed to screen additional patients for this trial.

A log of all patients enrolled into the trial (i.e. who have signed informed consent) will be maintained in the Investigator Site File (ISF) irrespective of whether they have been treated with investigational drug or not.

If a patient is enrolled in error (does not meet all inclusion criteria or meets one or more exclusion criteria on the day of enrolment), the sponsor should be contacted immediately.

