7.2.2 Primary endpoint analyses

The primary endpoint is the annual rate of decline in FVC [mL] over 52 weeks. The primary analysis will be based on all randomized patients who received at least one dose of trial medication, using all available data from baseline (excluded) up to Week 52, including visits done after premature treatment discontinuation, EOT visits and follow-up visits done before Week 52 (i.e. including all measurements after first drug intake and before or on day 373). The primary analysis will use a restricted maximum likelihood (REML)-based approach with a random slope and intercept model. The analysis includes fixed effects for treatment, HRCT pattern, and baseline FVC [mL], as well as the treatment-by-time and baseline-by-time interactions. Random effects will be included for the patient response for both time and intercept. Baseline FVC in mL will be included as a covariate in the analysis model. Baseline FVC is defined as the FVC result recorded at Visit 2, unless missing in which case the screening result will be used. The HRCT pattern (“UIP-like fibrotic pattern” or “Other fibrotic patterns”) will also be used as a covariate for the analysis performed. The point estimate of treatment difference between the nintedanib and placebo group will be provided as well as 95%CI. No statistical testing will be performed.

A sensitivity analysis including only on-treatment measurements of FVC (ml) will be presented. The same model as for the primary analysis will be used. This model implies that data are assumed to be missing at random (MAR) and it is implicitly supposed that patients who dropout would have behaved similarly to those who remained in the study.

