4. CHANGES IN THE PLANNED ANALYSIS OF THE STUDY

4.1 CLARIFICATION

- Comparing with the INBUILD trial (1199-0247), the duration of treatment of this study is only 52 weeks. The primary endpoint will include data collected up to last treatment visit, instead of day 373.
- The main analysis for primary efficacy endpoint of this study will be based on the treated set (according to randomized treatment), using all available data from baseline (excluded) up to week 52 visit. For patients who prematurely discontinued study treatment, data collected at follow-up visit and visits after treatment discontinuation will be included in the analysis.

- Due to the possible occurrence of mis-stratifications during the randomization process, the HRCT pattern as reported in the eCRF will be used in all analyses.
- Three patients were randomized by mistake, whose HRCT pattern was recorded incorrectly in the Interactive Response Technology (IRT) system. Two patients were randomized under “other HRCT fibrotic patterns” and the other one was randomized under “HRCT with UIP-like fibrotic pattern only”. They will be counted in the subpopulation of patients as collected in the eCRF in all analyses within the CTR.

[figure not shown]

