6. GENERAL ANALYSIS DEFINITIONS

6.1 TREATMENT(S)

For the definition of treatment administered during the trial, see Section 4 of CTP.

- Screening: From informed consent to randomization
- Treatment period: From first trial drug intake to last trial drug intake
- Residual effect period / Safety follow-up: From the last trial drug intake plus 1 day to last trial drug intake plus 7 days
- Off-treatment period: From start date of trial drug interruption to re-start of trial drug

All analyses will be based on the planned treatment groups (Nintedanib 150 mg bid vs. Placebo) as randomized by IRT. The subjects will be analyzed according to the stratum to which they actually belong to, regardless of any stratification error at randomization.

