7.4 PRIMARY OBJECTIVE ANALYSIS

7.4.1 Main analysis

The primary efficacy endpoint is the annual rate of decline in Forced Vital Capacity (FVC; expressed in mL) over 52 weeks. The main analysis will be based on the TS (according to randomized treatment), using all available data from baseline (excluded) up to week 52 visit. For patients who prematurely discontinued study treatment, data collected at follow-up visit and visits after treatment discontinuation will be included in the analysis. For patients who had multiple FVC measurements on the same day, the last measurement will be used in the analysis. Intercurrent event handling strategies for main analysis are described in [Section 6.3](#).

The main analysis uses a restricted maximum likelihood (REML) based approach with a random slope and intercept model. The analysis will include the fixed, categorical effects of treatment, HRCT pattern at baseline, fixed continuous effects of time and baseline FVC as well as the treatment-by-time and baseline-by-time interactions. Random effects will be included for patient response for both time and intercept. The HRCT pattern at baseline collected in eCRF will be used in the analysis.

The statistical model can be written as follows:

$$y_{ijkm} = (a_i + \vartheta_m + \beta_0 S_i + \tau_k) + (g_i + \beta_s S_i + \varphi_k) t_{ij} + e_{ij}$$

$$\begin{aligned}(a_i, g_i) &\sim N_2 (\mathbf{0}, \Sigma) \\ &\text{iid} \\ e_{ij} &\sim N (0, \sigma^2)\end{aligned}$$

The components of the model are as follows:

y_{ijkm} = FVC for patient i with HRCT pattern m at time j receiving treatment k
 a_i = random intercept effect for patient i, $i=1,2,\dots$
 ϑ_m = intercept coefficient of HRCT pattern m, $m=1,2$. (“other HRCT fibrotic patterns” as the class reference)
 β_0 = intercept coefficient of baseline FVC
 S_i = baseline FVC measurement for patient i
 τ_k = intercept coefficient of the effect of treatment k, $k=1,2$
 g_i = random slope effect for patient i
 β_s = slope coefficient of baseline FVC
 φ_k = slope coefficient of the effect of treatment k
 t_{ij} = time of measurement j for patient i, $j= 1,2,\dots J_i$
 e_{ij} = the random error associated with the time j of patient i. Measurement errors are independent and normally distributed with mean 0 and variance σ^2 , and uncorrelated with a_i and g_i .
 Σ = a 2x2 unstructured covariance matrix

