Within patient errors are assumed to follow a random coefficient regression model with random effect for intercept and slope. An unstructured variance-covariance structure will be used to model these random slope and intercept. The Kenward-Roger approximation will be used to estimate denominator degrees of freedom and adjust standard errors.

In case of model non-convergence, methods to overcome the issue are described in [Section 10.1](#). The first model to converge will be used as the main analysis on the primary endpoint.

The point estimate of treatment difference between the nintedanib and placebo group as well as two-sided 95% CI will be provided. No formal statistical testing will be performed. The primary treatment comparison of slopes will be assessed through the treatment-by-time interaction coefficient.

[figure not shown]
SAS code specifications are included in [Section 10.2](#).

**Boehringer Ingelheim
TRIAL STATISTICAL ANALYSIS PLAN
1199-0434**

Page 17 of 33

c40328414-01

Proprietary confidential information © 2025 Boehringer Ingelheim International GmbH or one or more of its affiliated companies.

**Boehringer Ingelheim
TRIAL STATISTICAL ANALYSIS PLAN
1199-0434**

Page 18 of 33

c40328414-01

Proprietary confidential information © 2025 Boehringer Ingelheim International GmbH or one or more of its affiliated companies.

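### Does the primary slope model need an HRCT pattern-by-time term because the stratification factor enters only through the intercept?

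*SAP*

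**What the plan says.** SAP 7.4.1 specifies a random slope and intercept model with categorical effects of treatment and HRCT pattern, plus "fixed continuous effects of time and baseline FVC as well as the treatment-by-time and baseline-by-time interactions". In the model equation, HRCT pattern appears once, as "intercept coefficient of HRCT pattern m". The slope bracket holds only the random slope, baseline FVC and treatment. The result is defined on the slope: "The primary treatment comparison of slopes will be assessed through the treatment-by-time interaction coefficient".

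Protocol 7.2.2 lists the same effects: "fixed effects for treatment, HRCT pattern, and baseline FVC [mL], as well as the treatment-by-time and baseline-by-time interactions". Protocol 7.2 declares all efficacy analyses exploratory and without testing, so the output is a point estimate with a 95% CI.

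On the factor itself, Protocol 3.3 says of the planned two-thirds UIP-like share: "This will allow for a certain enrichment of patients with more rapid progression, as has been shown in INBUILD". SAP 4.1 reports: "Three patients were randomized by mistake, whose HRCT pattern was recorded incorrectly in the Interactive Response Technology (IRT) system". Two of them were randomised under the other-pattern stratum and one under the UIP-like stratum. SAP 6.1 adds: "The subjects will be analyzed according to the stratum to which they actually belong to, regardless of any stratification error at randomization".

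**The concern.** Three facts together suggest an omission. The result is a difference in slopes, and baseline FVC is adjusted for on both intercept and slope, yet the one factor used to stratify the randomisation is adjusted for on the intercept only. The protocol itself links that factor to the speed of decline. And the SAP's decision to analyse by actual pattern after three stratification errors reaches, in this model, only the intercept.

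If UIP-like patients declined much faster and the arms differed noticeably in UIP-like share, part of the reported slope difference would reflect case mix. With no test and no secondary endpoint, the point estimate and its interval are the whole efficacy result, so even a moderate shift would matter. The apparent remedy is cheap: one supportive run with an added pattern-by-time effect.

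**Working it through.** **1. Scale of the result.** Protocol Table 7.5:1 gives an SE of 21.15 with 331 and 332 patients, so SD = 21.15/√(1/331 + 1/332) = 272.3 mL/year. For 60 vs 30, SE = 272.3 × √(1/60 + 1/30) = 60.9 and the 95% CI half-width is 1.96 × 60.9 = 119 mL/year. As a check, Φ((1−k) × 107/60.9), with k the required fraction of 107 mL/year (0.5, 0.4, 0.3), gives 0.810, 0.854 and 0.891. Table 7.5:2 states 0.817, 0.860 and 0.896, so the scale is right.

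**2. Imbalance from the three errors.** Assume IRT strata of 60 and 30 (the caps in Protocol 4.1.3) with exact 2:1 allocation in each. Actual UIP-like patients number 60 − 1 + 2 = 61. Let *s* be the UIP-like share on placebo minus that on nintedanib.

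| UIP-like, placebo / nintedanib | *s* | Probability |
|---|---|---|
| 19/30, 42/60 | −0.067 | 0.146 |
| 20/30, 41/60 | −0.017 | 0.444 |
| 21/30, 40/60 | +0.033 | 0.341 |
| 22/30, 39/60 | +0.083 | 0.069 |

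The mean is 0 and the RMS is 0.040. A mean of zero means no bias over the randomisation.

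**3. Slope gap between patterns.** The documents do not state it, but Protocol 1.2 gives relative reductions of 57% overall and "61% in patients with HRCT with UIP-like fibrotic pattern, and 49% for patients with other HRCT fibrotic patterns". With r = 106.96/187.78 = 0.5696, the UIP-like part of the total placebo decline is f = (0.5696 − 0.49)/(0.61 − 0.49) = 0.663. For an assumed INBUILD UIP-like share *w*, placebo decline is 187.78f/w (UIP-like) and 187.78(1−f)/(1−w) (other). Nintedanib decline is 0.39 and 0.51 times these. P and N are the UIP-like minus other gaps in decline on placebo and nintedanib.

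**4. Effect on the estimate.** With 30 and 60 patients, the placebo share lies 2s/3 above the overall share and the nintedanib share s/3 below it. The shift without the term is therefore s(2P+N)/3. A common pattern-by-time term estimates the weighted gap (P+2N)/3, so it removes s(P+2N)/3 and leaves s(P−N)/3.

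| *w* (assumed) | P | N | Weighted gap | RMS shift without term | RMS removed | RMS left |
|---|---|---|---|---|---|---|
| 60% | 49.6 | 0.4 | +16.8 | 1.34 | 0.68 | 0.66 |
| 64% | 19.0 | −13.6 | −2.8 | 0.33 | 0.11 | 0.44 |
| two thirds | −2.8 | −23.8 | −16.8 | 0.40 | 0.68 | 0.28 |

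All gaps and shifts are in mL/year. At 60% the term halves a shift of 0.02 SE (1.34/60.9). At 64% it moves the estimate further away. At two thirds it overshoots, removing 0.68 against a shift of 0.40. Rounding of the percentages alone moves the weighted gap between −4 and 38 at 60%, and between −39 and 6 at two thirds, so even its sign is not known.

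**5. Precision.** If pattern does not affect slope, the term raises the SE by 0.09% on average over the splits in step 2, or about 0.18% in variance. The gain is (2/9)D²/272.3² for a weighted gap D. Break-even is D = 272.3 × √(0.0018 × 4.5) ≈ 24 mL/year, above the ±16.8 found in step 4.

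**6. Could the second run be read?** In simulations of the two models (600 runs per setting, assumed 15% dropout and assumed variance components), mean SEs were 65.18 without and 65.23 with the term at 60%, and CI coverage was 97.2% and 97.0%. The two estimates differed by RMS 3.6–3.7 mL/year. The imbalance removed accounts for only 0.68²/3.65² = 3.5% of that squared difference. Using instead the SE cost in step 5, the noise is about 60.9 × √0.0018 = 2.6 mL/year and the ratio is 0.68²/2.6² = 7%. On either figure, the gap between the two runs would be nearly all noise.

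**The case for a change.** The best case for adding the run is that the facts are right. The stratification factor is missing from the slope part, the protocol treats it as prognostic for slope, and perfect balance is impossible under the assumptions of step 2. A reader of SAP 4.1 will ask whether the errors touched the slope difference, and one term answers this with no new data. Since it adds no treatment-by-pattern effect, it does not conflict with the decision to plan no subgroup analysis. The slope gap could also be larger than derived here. With common gaps of 50 and 100 mL/year, the RMS shift is 0.040 × 50 = 2.0 and 0.040 × 100 = 4.0 mL/year. In the worst split (probability 0.069) it is 0.083 × 50 ≈ 4 and 0.083 × 100 ≈ 8 mL/year.

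The description of the model stands. The need for the run does not follow. Even 8 mL/year is small beside a half-width of 119, and those gaps are illustrative upper values. Nor can a common pattern-by-time term show whether the treatment effect on slope depends on pattern: that would need a treatment-by-pattern-by-time term. On the reader's question about SAP 4.1, step 2 already bounds the imbalance the three errors can cause. Finally, the public SAP copy does not show section 7.4.2 or sections 10.1 and 10.2, so it cannot be said that no such run is planned.

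**Conclusion.** The concern does not hold. The primary model contains the stratification factor, matches the protocol, gives an estimate that is unbiased over the randomisation and has a valid interval. Leaving pattern out of the slope part costs at most about 0.02 SE in RMS terms on the gaps derived from the protocol's own figures. The added term would remove about 0.01 SE of unknown sign, with no expected gain in precision. An extra run would be a matter of preference, not the repair of a defect.

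This rests on IRT strata of 60/30 with exact 2:1 allocation, an INBUILD UIP-like share between 60% and two thirds (not in the documents), and treating the adjusted INBUILD rates as simple weighted averages over pattern. A true common gap of 100 mL/year would raise the RMS shift to 4.0/60.9 = 0.07 SE, which still would not alter how the result is read.

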7.4.3 Supplementary analysis

A supplementary analysis including only on-treatment measurements of FVC (ml) will be analyzed. This analysis reflects the expected biologic effect of nintedanib 150 mg bid in the treatment of patients with PF-ILD.

FVC collected from the first drug administration up to the last drug intake plus one day will be included in analysis. The same RSI model used in the main analysis will be applied (see [Section 7.4.1](#)). Point estimate and two-sided 95% CI of the treatment effect will be presented. Tables presenting the results of the supplementary analysis will be created in addition to graphical representations.

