In case of clinically significant deterioration, initiation of additional therapy for ILD i.e. on top of the study medication is allowed after completion of the 6-month study visit (Visit 7) as described in [Table 4.2.2.1:1](#), as determined by the Investigator. For example, introduction of additional therapy may be considered if the patient experiences $\geq 10\%$ relative decline in FVC% pred from baseline that is not attributed to a reversible process (i.e. respiratory infection). Detailed (S)AE information following such events should be recorded in the eCRF. Please also refer to cautionary notes ([Section 4.2.2.2](#)).

Prohibited medications

As detailed in the exclusion criteria, patients receiving *pirfenidone, nintedanib, full dose therapeutic anticoagulation or high dose antiplatelet therapy* (e.g. acetyl salicylic acid >325 mg/day, or clopidogrel >75 mg/day, or equivalent doses of other antiplatelet therapy) are not eligible for participation in the study.

The use of pirfenidone and nintedanib are prohibited throughout the study, including the Follow-up period.

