6.3 INTERCURRENT EVENTS

Intercurrent events and handling strategies with respect to the primary efficacy endpoint are described in [Table 6.3:1](#).

For the main analysis, intercurrent events such as premature treatment discontinuation and restricted medication use will be handled by applying treatment policy strategy, i.e., all available data collected up to week 52 visit will be included in the analysis.

Death will be handled by applying while-alive strategy, i.e., data collected while patient is alive will be included in analysis.

The use of Pirfenidone and Nintedanib (non-IMP prescribed by investigator) are prohibited during the trial and considered as important protocol violations. In the supplementary analysis, prohibited medication and restricted medication will be handled by applying while-on-treatment strategy, i.e., data collected after the initiation of prohibited or restricted medication will not be included in the analysis.

Further details of intercurrent event handling strategies will be described in [Section 7](#).

Table 6.3: 1 Intercurrent events and handling strategies

Intercurrent event	Main analysis strategy	Supplementary strategy
Treatment discontinuation	Treatment policy	While-on-treatment
Initiation of restricted medication	Treatment policy	While-on-treatment
Initiation of prohibited medication	Treatment policy	While-on-treatment
Death	While-alive	While-alive

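### The data rule for the supplementary FVC analysis (SAP 7.4.3) omits the cut at restricted or prohibited medication that SAP 6.3 declares for the same analysis

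*SAP*

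**What the plan says.** SAP 6.3 and Table 6.3:1 list treatment discontinuation, restricted medication and prohibited medication as separate intercurrent events. Each is handled by treatment policy in the main analysis and by a while-on-treatment strategy in the supplementary one. For the two medication events, 6.3 spells the strategy out: "data collected after the initiation of prohibited or restricted medication will not be included in the analysis". It then passes the detail on: "Further details of intercurrent event handling strategies will be described in" Section 7.

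In Section 7, the main analysis points back: "Intercurrent event handling strategies for main analysis are described in" Section 6.3 (SAP 7.4.1). The supplementary analysis does not. SAP 7.4.3 gives its own rule: "FVC collected from the first drug administration up to the last drug intake plus one day will be included in analysis". Its only reference is to 7.4.1, for the model. It states its purpose as follows: "This analysis reflects the expected biologic effect of nintedanib 150 mg bid in the treatment of patients with PF-ILD".

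Protocol 7.2.2 promises less detail: "A sensitivity analysis including only on-treatment measurements of FVC (ml) will be presented". It has no medication cut. SAP 6.1 defines the treatment period by trial drug intake alone.

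For a patient who worsens markedly, protocol 4.2.2.1 provides that "initiation of additional therapy for ILD i.e. on top of the study medication is allowed after completion of the 6-month study visit (Visit 7". Its example trigger is a fall of at least 10%, described as a "relative decline in FVC% pred from baseline that is not attributed to a reversible process".

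**The concern.** Two sections give different inclusion rules for one analysis. The section that a programmer would work from is the one without the medication cut. The cut on last drug intake does not stand in for it, because the protocol allows the added therapy while trial drug continues. SAP 6.1 does not bring the cut in through the term on-treatment either.

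What is at stake is the interpretation of the supplementary estimate. It is presented as reflecting the biologic effect of nintedanib. Under 7.4.3 alone it would keep FVC measured on added ILD therapy, and under 6.3 it would not. The protocol's example trigger is an FVC decline, which is expected more often on placebo, so the choice need not be neutral between arms. If the rule is left open, it could be settled after the results are known.

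**Working it through.** **1. The two rules for the same patient.** By protocol 6.2.2 and the Flow Chart, scheduled post-baseline FVC falls at weeks 2, 4, 6, 12, 24, 36 and 52. Take a patient who stays on trial drug to week 52 and starts restricted therapy. Sxx is the sum of squared deviations of the visit weeks from their mean, which governs how much the patient tells us about slope.

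| Start of therapy | Rule | Values kept | Sxx | Share of full |
|---|---|---|---|---|
| just after week 24 | 7.4.3 | 7 | 4776 - 136²/7 = 2133.7 | 100% |
| just after week 24 | 6.3 | 5 | 776 - 48²/5 = 315.2 | 14.8% |
| just after week 36 | 6.3 | 6 | 2072 - 84²/6 = 896.0 | 42.0% |

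So the datasets differ, and the values in dispute are the late ones that carry most of the slope information. Restricted drugs are barred for the first six months, so permitted use touches only weeks 36 and 52.

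**2. Precision of the trial, for scale.** No stated figure is in dispute. Protocol 7.5 gives 81.7% probability of an estimate of at least 53.5 mL/year when the true effect is 107. The implied SE is (107 - 53.5)/z(0.817) = 59.2 mL/year. As a check from the pivotal trial: SD = 21.15/√(1/331 + 1/332) = 272.3, and SE = 272.3 × √(1/60 + 1/30) = 60.9, which gives 81.0%. The two agree closely.

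**3. How far the rules can diverge.** The documents give no rescue rate and no effect of rescue on FVC, so everything here is assumed:

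- Mean slopes are -187.78 and -80.82 mL/year (protocol Table 7.5:1).
- Baseline FVC is 2000-2500 mL, so a 10% fall is 200-250 mL.
- Residual SD is 80 mL and intercept SD is 100 mL.
- Random-slope SD is √(264.7² - 80² × 52²/2133.7) = 249 mL/year, where 264.7 = 59.2/√(1/60 + 1/30).
- There is no dropout.
- 25-50% of patients with such a fall at week 24 or 36 start restricted therapy.

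Simulated 60-versus-30 trials were fitted by a random slope and intercept model with variances held at these values. About 9-12 of 30 placebo and 12-17 of 60 nintedanib patients meet the decline trigger, and 2-6 and 3-8 of them start therapy. Let D be the FVC gain from the added therapy. The table gives the treatment difference under 7.4.3 minus that under 6.3.

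| D (mL) | Mean shift (mL/year) | Single-trial SD (mL/year) |
|---|---|---|
| 0 | 0.0 to +0.5 | 8-14 |
| 100 | -2.7 to -6.7 | not tabulated |
| 200 | -5.9 to -13.9 | 14-23 |

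At D = 0 the two rules agree on average, but in one trial they differ with an SD of 8/59.2 to 14/59.2, about 0.14 to 0.24 SE. A small full REML check (150 runs, 200 mL threshold, 50% uptake) gave 0.0 at D = 0, -8.4 (Monte Carlo SE 1.2) at D = 100 and -12.4 (Monte Carlo SE 1.8) at D = 200. These are compatible with the table within simulation error.

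**4. Cost of the cut.** In the same simulation, applying the 6.3 cut raises the SE from 59.2 to 59.7-60.8 mL/year: 0.5/59.2 to 1.6/59.2, or 1-3%.

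**The case against.** The strongest reply is that the SAP already contains the rule. Section 6.3 does more than name a strategy: it says which data are left out of the supplementary analysis. Section 7.4.3 can be read as setting the trial-drug window, with 6.3 removing post-medication values inside it. That joint reading gives the earlier of the two cuts, which is what the fix asks for. This stands, and it limits the point to a missing statement and cross-reference. But 7.4.3 says without qualification that values up to its cut-off are included, and nothing tells the reader to apply 6.3 as well.

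Other parts of the reply also stand. SAP 7.4.2 and the SAS specifications in Section 10.2 are not visible, so the cut may be written there. SAP 6.2 places the handling of important protocol deviations in separate specifications, and SAP 7.2 says prohibited medication is documented in one. The prohibited-drug part of the gap may therefore be closed outside the published text.

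A reader might infer more than the documents support:

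- *That 7.4.3 biases the estimate against nintedanib by a known amount.* Any mean shift needs D above 0. Protocol 4.2.2.1 justifies the prohibition by saying that eligible patients have progressed on these drugs and do not, or no longer, benefit from them. On that premise D is near 0.
- *That the last-intake cut never removes FVC measured on added therapy.* It does once a patient stops trial drug.
- *That parenteral steroid rescue escapes the restricted list.* SAP 7.2 cites the whole of protocol 4.2.2, which also names oral steroids without a dose and high-dose steroids without a route. The documents never mention parenteral steroids, and all concomitant medication is tabulated by ATC3 class and arm.

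**Conclusion.** The inconsistency is real and minor. On the visible text, SAP 7.4.3 followed alone does not carry out the while-on-treatment strategy that SAP 6.3 and Table 6.3:1 declare for restricted and prohibited medication. Followed together, the two sections do.

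The primary treatment-policy analysis is unaffected, and protocol 7.2 makes every efficacy analysis exploratory with no testing. The size of the effect on the supplementary estimate is unknown. If the added therapy has no FVC effect, the mean shift is near 0. Even then, under the assumed rescue rates, the single-trial estimate would depend on the rule chosen with an SD of roughly 8-14 mL/year. The figures for D above 0 are illustrations only. That the two sections state different rules can be read directly from the text; the magnitude rests wholly on assumption.

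**What to change.** Before treatment information is released, amend SAP 7.4.3 to say that FVC is included from first drug administration up to the earlier of (a) last drug intake plus one day and (b) first initiation of restricted or prohibited medication, as set out in Section 6.3. Report by arm how many patients and how many FVC values cut (b) removes beyond cut (a). If those counts are near zero, the reader can see that the choice did not matter.

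The cost is one sentence, a cross-reference, the matching program specification and a small table. Patient care, data collection and the primary analysis do not change. The downside is slightly less data (SE about 1-3% larger under the assumptions above), and values after worsening leave an analysis that then relies on missing at random beyond the cut. If the sponsor prefers to keep those values, the alternative is to change 6.3 and Table 6.3:1 to treatment policy for the two medication events in the supplementary analysis, so that both sections still agree.
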